After the completion of the conferences, we will plan and host a CDU online conference (Month 15) in which the participants will present their experience and conferences presentations to the university audience and community members. After fulfilling all requirements of the program, they will be compensated with \$200 digital gift card and certificate for their time and participation. Scheduling of the CSC for CWWs monthly sessions will be accordance with the preference of the program participants. In addition, a focus group will be scheduled in Month 15 for the CWWs participants to discuss program outcomes and share experiences of community-led conferences, in addition to perspectives of future directions for community-led research in cancer survivorship and caregiving. CWWs can receive a \$50 digital gift card for participation in this focus group.

Phase IV: The investigators will then convene throughout months 15-16 to evaluate performance data, review strategies, discuss barriers and success, and update materials and resources for future CSCLENS program cycles.

IV. Risk/Benefit Assessment

9. Benefits to participants: What is the risk benefit ratio of this research, compared with available alternatives? Describe the potential benefits the participants may receive as a result of their participation in the research. *The potential benefits of the research must justify the risks to human participants. The risk benefit ratio of the research must be at least as favorable for the participants as that presented by standard treatments for their condition. When comparing the risk/benefit ratio of research with that of available alternatives, the alternative of doing nothing should be included in the analysis.*

The benefit of this program to the participants is that they will gain knowledge of cancer survivorship and caregiving program.

10. Benefits to society: What benefits to society and the community may be expected?

This study will help the society by providing training to clergy wives and widows as community leaders who are well prepared to manage the complexity faced by cancer survivors and caregivers. These individuals will support the acquisition of knowledge to care for cancer survivors and their caregivers.

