11. Risk to participants: Describe any potential risks or likely adverse effects of the drugs, biologics, devices or procedures participants may encounter in the study. State the potential risks – physical, psychological, social, legal or other – connected with the proposed procedures and assess their likelihood and seriousness. And state the breach of confidentiality, distress due to questioning, etc.

There is no obvious risk for the participant. However, some participants may experience sadness over the pain experienced by cancer patients that they come in contact with. If that happens, the research team, which has an experienced mental health nurse will provide initial screening and counseling. We will also refer the participant to consult with his/her physician for more in-depth care as necessary.

The research team will be contacting participants via email as well as emailing them a copy of their signed consent form. This may include sensitive information (i.e. name) and identification that they are participating in a study about cancer. We will do our best to ensure that this information is confidential, and data is secured, but there is always risk for data security.

12. Confidentiality:

- How will the data be collected and recorded? How will the data be coded to protect personal privacy?

All focus group interviews will be audio-recorded. All interviews will be transcribed verbatim and coded from data codebook developed from the data through an iterative process with all the PIs.

Data Collection

Focus Groups: An experienced facilitator will conduct three focus group sessions with URM cancer survivors, caregivers and clergy wives and widows. We will use a semi-structured interview guide to assess: 1) their biopsychosocial and spiritual health needs, 2) perceived barriers for optimal quality of life and health, and 3) their ability to obtain external support and resources, 4) perceived challenges in their care based on their age and minority status, and 5) Experiences and impact of participation in the study. The interview guide is provided. The focus group interviews will be audio recorded.

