Focus Group Demographic Questionnaire: This will include mostly demographic questions which center on the age, gender, education, race/ethnicity, and family income of the participant. The participant must also identify if they are a cancer survivor or cancer caregiver or both. If a cancer survivor, the participant will be asked about the cancer diagnosis and staging, length of disease, time since remission or last treatment, comorbidities and chronic health conditions, and types of cancer treatment received (chemotherapy, radiation, surgery, other (specify)). If a caregiver, they will provide length of caregiving and caregiver training, involvement in nursing or medical care of CR, performance of nursing/medical care activities relationship to care recipient, diagnosis of care recipient, health status and chronic conditions hours spent with care recipient each day.

CSC for CWWs Demographic Questionnaire: Demographic information about each CSCLENS program participant will be collected prior to the CSC for CWWs program. Data will include the participant's age, gender, race/ethnicity, enrolled nursing program, years of experience in healthcare industry, and cancer survivor and/or caregiver status.

Cancer Survivorship and Cancer Caregiving Self-Efficacy Survey: Each CSC for CWWs program participant will complete the Cancer Survivorship Self-efficacy and Cancer Caregiving Self-Efficacy survey prior to the beginning of the CSC for CWWs program (T0) and at the completion of the CSC for CWWs program (T1). The instrument is a brief, Likert scale with values ranging from 0-4 for each of the nine questions related to cancer survivors and caregivers' health needs, psychosocial support, and nursing care plan education, with a total score of 36 (Appendix B & C). Final scores will be computed for each participant by the sum of correct answers.

Nursing Cancer Survivorship Care Knowledge Survey: This survey, adapted from Lester, Wessels, & Jung (2012) focuses on knowledge about cancer survivorship concepts, cancer treatment and side effects, survivorship issues, and comfort care⁴⁰. All CSC for CWWs participants will complete the survey prior to the beginning of the CSC for CWWs program (T0) and at the completion of the CSC for CWWs program (T1). This measure is a Likert scale with values ranging from 0-4 for each of the 35 questions (Appendix D)

CWW-Led Conference Surveys:

: We will utilize the following surveys:

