c. Who will have access to the data and the data codes? If data with participant identifiers will be released, specify the person(s) and agencies to whom this information will be released?

The only people who will have access to the data and data codes will be the members of the research team... PI [name], Co-Investigator [name] and Research Assistant [name].

d. What will happen to the data when the study is completed? How long would the data exist before destroying it?

All study data will be shredded and destroyed after the study is completed. Data will be kept for seven years before destruction.

V. Data Analysis

13. Analysis: Please delineate the data analysis plans for this study. Include planned statistical analyses and explanation of determination sample size. What statistical test will be used?

Qualitative data obtained from the audio recordings of focus group will be transcribed verbatim. To facilitate data analysis, the data will be entered into the qualitative data software, NVivo or Atlas.ti. Data coding will begin with the reading of the transcripts by the PIs to identify the preliminary codes. Data analysis will continue with a three-level coding process: 1) open coding to identify patterns in the transcripts, 2) focused coding to explore clustered concepts, and 3) identification of major themes. A coding manual will be created in an iterative process and independently coded by all three PIs to establish inter-rater reliability. All transcripts will initially be coded by the PI and Co-I. The themes that are developed will be used to inform the CSC for CWWs curriculum and content outline and care plan assessment.

For all quantitative data analyses, sample demographic characteristics for the CSC for CWWs program and workshops will be calculated. Descriptive statistics (e.g., frequencies, central tendencies, and variabilities) will be completed for the all surveys and summarized using means, medians and other quantiles, standard deviations, interquartile range, minimum and maximum, as well as graphically (e.g., boxplots). Data will be examined for outliers and tested

for normality, linearity, and homoscedasticity. Bivariate and multivariate analysis for CSC for CWWs will be completed for trends by age and gender.

VI. Limitations of the Study

14. Indicate any limitations of your project.

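### The women are surveyed before and after the program, but section 13 plans no analysis of within-woman change (T1 minus T0)

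*Combined protocol and SAP*

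**What the plan says.** **Design.** Section 12 (Data Collection) has each program participant complete the self-efficacy surveys "prior to the beginning of the CSC for CWWs program (T0) and at the completion of the CSC for CWWs program (T1"). The knowledge survey follows the same schedule: "All CSC for CWWs participants will complete the survey prior to the beginning", and again at completion. Section 8 (Phase III) also describes the self-efficacy questionnaires as pre and post. The target is to recruit and retain 50 women.

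**Scoring.** The self-efficacy instrument has nine items scored 0 to 4 and a total of 36. The scoring rule reads: "Final scores will be computed for each participant by the sum of correct answers". The knowledge survey has 35 items scored 0 to 4, and no total is given.

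**Analysis.** The form asks the investigators, "What statistical test will be used". For the quantitative data, section 13 answers: "Descriptive statistics (e.g., frequencies, central tendencies, and variabilities) will be completed for the all surveys". It lists means, medians, SDs, ranges and boxplots, and checks for outliers, normality, linearity and homoscedasticity. The only further analysis is this: "Bivariate and multivariate analysis for CSC for CWWs will be completed for trends by age and gender".

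**Linkage.** Section 12 asks, "How will the data be coded to protect personal privacy". The answer describes only the focus group recordings and their codebook. Data codes are mentioned later in section 12, under access to data, but are not defined.

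**The concern.** In a one-group pre/post design, the change within each woman is the natural quantity to report. Nothing in section 13 is defined on it. The SDs are for the surveys, not for the difference between two surveys. The outcome of the age and gender analysis is not stated (T0, T1 or change), and gender can hardly vary in a group defined as wives and widows. Normality and homoscedasticity are to be checked, but the analysis they serve is not named.

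The SDs at T0 and T1 do not determine the SD of change; their correlation is also needed. So a report that follows section 13 would give two means and two SDs, and would not show whether most women moved a little or some rose while others fell. The Timetable plans journal articles and an R01 application. The design of that later study is not given, but if change is an outcome there, the SD of change is a planning input that this pilot could supply and, as written, would not report.

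**Working it through.** **Inputs from the documents.** n = 50 (section 8, recruitment and retention target); self-efficacy range 9 × 4 = 36, which matches the stated total. The documents give no SD, T0-T1 correlation, effect size or power, so the 50 cannot be reproduced from a formula and there is no planned precision to compare with.

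**Assumptions.** All 50 women have both surveys; descriptives are given at each time point; the SD is the same at T0 and T1 (call it 1 SD); the correlation r is 0.3, 0.5 or 0.7.

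**Step 1: mean change.** With all 50 retained, the mean of T1 minus T0 equals the T1 mean minus the T0 mean. The planned summaries give it.

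**Step 2: SD of change.** SD of change = √(2(1 − r)).
- r = 0.3: √1.4 = 1.18 SD
- r = 0.5: √1.0 = 1.00 SD
- r = 0.7: √0.6 = 0.77 SD

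Identical planned summaries are thus compatible with variances of change that differ by a factor of 1.4/0.6 = 2.3.

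**Step 3: 95% CI half-width if the two summaries are treated as independent.** t(0.975, 98) × √(2/50) = 1.984 × 0.200 = 0.397 SD, whatever r is.

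**Step 4: 95% CI half-width from 50 linked pairs.** t(0.975, 49) × √(2(1 − r)/50), with t = 2.010.

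| r | Paired half-width | Share of 0.397 |
|---|---|---|
| 0.3 | 0.336 SD | 85% |
| 0.5 | 0.284 SD | 72% |
| 0.7 | 0.220 SD | 55% |

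At r = 0 the paired half-width is 0.402 SD, so pairing gains nothing there.

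**Step 5: the dates that define T1.** T1 is tied to program completion, so the program's length fixes the interval over which change is measured. The documents give it in several ways: a year-long program (section 5); six months (section 8, Phase II); Months 9-15, and also ten months (section 8, Phase III); Months 5-11 (Timetable). These need to be reconciled.

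**Step 6: the aim served.** Section 8 (Phase III) places the program and its pre/post questionnaires under Aim 2. Section 5 assigns Aim 2 to the focus group analysis in Phase II and Aim 3 to the training program. So the documents do not settle which aim the change scores serve.

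**The case against.** The strongest reply is that this is a feasibility pilot with no hypothesis about score change, so descriptive reporting is enough. That stands, and it is a reason not to ask for a list of tests or models. It does not remove the point: a mean change with its SD and interval is itself descriptive, and it is the description that fits repeated surveys of the same women.

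Two stronger readings are tempting, and the documents support neither.

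- **That the report would carry no measure of uncertainty.** The planned SDs and n do allow an interval that treats the time points as independent, and it is conservative if the correlation is positive. What is missing is the sharper interval and the spread of individual change. If the forms are linked, both could still be computed from the raw data, which section 12 keeps for seven years.
- **That the forms are unlinked and the pairs will be lost.** The text does not state a common identifier, but much in it points to one. Consent is individually signed, completion credit depends on consent to data collection, and scores are computed for each participant. Payment is tracked too: "After fulfilling all requirements of the program, they will be compensated with" a gift card. The age trend also needs the demographic form, collected before the program, to be joined to any survey score analysed. The appendices with the forms are not in the text available for review, so an ID field cannot be ruled out.

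A reader might also expect bias from missing T1 surveys. The documents give no drop-out rate or pattern, so no size can be attached to it. Reporting how many women have T0, T1 and both is a sufficient safeguard here.

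**Conclusion.** The omission is real and modest. Section 13 plans no analysis of T1 minus T0, although the same women are surveyed twice. Followed as written, it supports a half-width of about 0.40 SD for the mean change, where 50 linked pairs would give 0.34, 0.28 or 0.22 SD at correlations of 0.3, 0.5 or 0.7. It also leaves the variation in change between women unreported.

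The figures rest on equal SDs, full retention of 50 and assumed correlations; none of the correlations comes from the documents. That section 13 omits the analysis needs no assumption.

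Whether the T0 and T1 forms share an identifier is a point to confirm, not a shown defect. It is the one time-critical part, because pairs may not be recoverable if T0 is collected without a code. The point should be addressed, but it does not threaten the pilot.

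**What to change.** 1. In section 13, state as the main quantitative summary the within-woman change (T1 minus T0) for each self-efficacy scale and for the knowledge survey. Report the mean, SD, paired 95% CI and the numbers of women with T0, T1 and both.
2. Confirm before T0 that both forms carry the same study ID. Word this for any collection mode, since no section says how these particular surveys are administered.
3. Score the 0-4 self-efficacy items as the sum of item scores (0 to 36) in place of a count of correct answers, and state the total for the knowledge survey.
4. For the age trend, use T1 adjusted for T0 as the outcome. Drop gender unless it varies among the participants.
5. Reconcile the program dates that define T1 (section 5, section 8 Phases II and III, Timetable) and the aim that the surveys serve (sections 5 and 8).

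**Cost:** a few sentences, an ID on both forms if not already there, and slightly more analysis. No additional participants or surveys are needed, and the mean change itself is unaltered if all 50 women are retained.
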